The primary hypothesis is that 1) the Relational Agent will be more effective than TAU in reducing the quantity (drinks per day) and frequency (number of drinking days per week) of alcohol consumption.

The two secondary hypotheses are that 2) the Relational Agent will be more effective than TAU in improving rates of brief intervention; and 3) the Relational Agent will be more effective than TAU in improving rates of referral. Additional exploratory hypotheses are listed in the Analysis section.

(2) Background, Significance, and Relevance to Veteran's Health

Please see Aim 1 protocol and grant proposal.

(3) Work Accomplished

Please see grant proposal for pilot work. So far in this study we have completed part of Aim 1. We interviewed 20 veterans and collected information on their preferences for the appearance of the relational agent, as well as some information on how the setting should look. We are in the process of collecting feedback on the sections of the relational agent program that we have programmed so far and making final adjustments to the program.

(4) Work Proposed

Methods

Setting and Population

We will recruit a total of 180 Veterans from primary care clinics, both men and women. We expect to recruit approximately 10-40 participants per month over 11 months, finishing the 3 month follow-up visits in 14 months from the start of recruitment. The study will be conducted first in the Jamaica Plain primary care clinic (JP-PCC) of the VA Boston Healthcare System. If we are unable to meet our recruitment goals, we will also attempt to recruit at the West Roxbury primary care clinic (WRX-PCC) or Brockton primary care (BR-PCC). In any case, we will exclude the veterans who participated in Aim 1.

Recruitment

We are working collaboratively with the team leaders and clinic staff to identify a process by which Veterans who screen positive on the AUD-C can be referred to the research assistants without disruption to the workflow of primary care encounters. The usual practice in this setting is that the health technician or LPN administers the AUD-C and informs the physician if the Veteran has a positive screen. The physician (or other responsible primary care clinician) is then responsible for delivering the brief intervention. Per current practice, referral to Mental Health for alcohol problems is routinely made by computerized order to one of the specialty substance abuse clinics.

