In general, we approach this study as a pragmatic clinical trial, such that we intend to maximize inclusion to reflect actual clinical practice and to demonstrate effectiveness, rather than efficacy, of the intervention. Inclusion criteria include: (1) having a primary care provider at VA Boston PCC; (2) having a positive screen on the AUD-C; (3) drinking above CDC guidelines in the past 30 days; (4) willing to provide us with at least 1 "locator person" (and preferably 2 locator persons) who always knows their whereabouts (explanation on p. 5). Exclusion criteria are: (1) Veterans who do not have a valid telephone number and mailing address, and who expect to move in the next 6 months. This information is needed to ensure 3-month follow-up contact and completion of Aim #3; (2) Veterans who report less than 14 drinks per week or less than 5 drinks on any one occasion in the past 30 days when screened on the Quick Drink Screen (described in Measures). The purpose of adding this screening is to account for the fact that the AUD-C measures Veterans' alcohol consumption over the past year, and it is possible for Veterans to screen positive on the AUD-C but to have stopped drinking

during the past 30 days. We will use the Quick Drinking Screen (see Measures) to exclude these Veterans who screen positive on the AUD-C but are not consuming unhealthy quantities of alcohol at the time of the study, because the primary study outcomes include quantitative measures of alcohol consumption. These Veterans may not be currently in need of brief intervention because they have recently cut down their drinking. (3) Veterans who have participated in substance abuse treatment in the past 30 days because they are already receiving care.

The table below summarizes the eligibility criteria.

We note that the study will not exclude patients with mental illness, traumatic brain injury, or other mental or neurological conditions. Second, we will measure health literacy to ensure the program can be used by any Veteran, no matter their familiarity with health issues.

Study Eligibility Criteria	
Inclusion Criteria	Exclusion Criteria
AUD-C \geq 5	Participation in Aim 1 of the study
Receive primary care where recruited	Drank <14 drinks/wk and <5 drinks on one occasion in past 30 days
Drinking more than guidelines in past 30 days	Unsure of phone and address over next 6 months
Stable phone and address over next 6 months	Alcohol treatment in last 30 days

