The research assistants will conduct the 3-month follow-up interview by telephone with each enrolled study participant. Each of these telephone interviews will take approximately 15 minutes and will include completion of the QDS and SIP. The research assistant will also ask whether the Veteran received brief intervention or referral for alcohol problems at the index primary care visit or in the intervening 3-month period; this ascertainment will complement the documentation of brief intervention and referral that may be present in the computerized patient record system (CPRS). In addition, the research assistant will ask about Veterans’ satisfaction with care for alcohol problems in PCC. Veterans receive \$20 in appreciation for their participation in completing the 3 month follow-up interview.

Follow-up Procedures

To minimize loss-to-follow-up and maximize participation, we will send each participant a reminder letter approximately one week prior to each interview. We also leave a reminder call a few days before. [name] will train the research assistants to conduct the in-person and 3 month telephone interviews and will monitor their quality and accuracy. The research assistants will follow a written protocol for conducting these calls, including a script (see Appendix B) for how to interact with automated telephone answering systems (machines or voice mail) and how to confirm the identity of the Veteran to ensure privacy and confidentiality. Based on our prior studies, we developed a protocol for multiple call attempts if the Veteran is unreachable, followed by up to 3 letters attempting to reschedule the missed appointments. If we are still unable to contact the participants we will send out the locator letters and follow them up with a phone call to the locator person(s). We will also check CPRS for changes in phone numbers or addresses, and to check if a participant is scheduled for a visit in the near future where we can speak with them. Data from each of these interviews will be entered into RedCAP on a study laptop computer (equipped with all required encryption and passwords) and eventually converted to Statistical Package for the Social Sciences Software (SPSS) data file format for statistical analysis.

Review of the Computerized Patient Record System (CPRS)

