Upon completion of the 3-month follow-up interview, we will review the electronic health record of each enrolled Veteran-participant to conduct a structured abstraction of key data elements for the statistical analysis. [name], [name] and study team members will develop a data collection form to guide the data abstraction process. Table 3 shows a partial list of the data elements to be abstracted from CPRS. We will closely follow the methodology of Hawkins et al, who developed and implemented a structured process to review and abstract data on brief intervention and referral for alcohol treatment from CPRS.⁷ In that study, trained medical record reviewers used computerized algorithms to ensure reliable and accurate data abstraction. Their

reviewers recorded documented brief intervention with the following standardized instructions: “At any time since the most recent alcohol screening, does the record document any of the following components of brief alcohol counseling for past-year drinkers? Indicate all that apply and the date counseling was noted in the record:

Patient drinks within recommended limits per self-report, (2) Advice to abstain, (3) Personalized counseling regarding relationship of alcohol to the patient’s specific health issues, (4) General alcohol-related counseling (not linked to patient’s issues), (5) Patient advised to drink within recommended limits, (6) No alcohol counseling documented.”

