Alcohol use and related behaviors will be assessed by in-person survey at baseline and by telephone survey at 3 months after randomization. Principal intervention effect analyses will be performed at 3 months. The primary dependent (outcome) variables are number of drinking days per week (frequency) and average drinks per drinking day (quantity). Secondary dependent variables are percent receiving brief intervention and percent referred for further evaluation or treatment of alcohol problems.

Independent Variables

The two independent variables are the experimental condition, Treatment as Usual vs. Treatment as Usual plus Relational Agent Intervention, and the severity of alcohol use, dichotomized as Risky Drinking vs. Alcohol Use Disorder. The experimental condition will be assigned by random allocation (see Section 4.e.7).

The severity of alcohol use variable, which will be used to allocate Veteran-participants into two strata prior to randomization, will be ascertained by the baseline completion of the MINI.

Dependent Variables

The primary dependent variables (i.e., the main study outcome measures) are **number of drinking days per week** and **average drinks per drinking day**. Because the Relational Agent will target reduction of both the frequency (number of drinking days per week) and the quantity (average drinks per drinking day) of alcohol consumption, each of these measures will be considered separately as primary outcome measures. These variables are measured by the QDS.

Secondary dependent variables include **completion of brief intervention** (yes/no) and **referral for evaluation/treatment** (yes/no); these secondary dependent variables will be ascertained from review of CPRS. We will also ascertain completion of brief intervention and referral for evaluation/treatment from the interviews with participants; we will assess concordance between CPRS and Veterans' self-report and, for main analyses, we will count brief intervention or referral as completed if they are ascertained from either source.

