GEE utilizes inverse probabilities to correct for any bias associated with NMCAR, with participants who are Completers weighted with the drop-out probabilities of participants with the “same” characteristics at Baseline. These weighting values will be estimated from the logistic analyses described above.

The overall design is a three-way mixed-design with Treatment Arm (Treatment as Usual vs. Treatment as Usual plus Relational Agent Intervention) and Drinking Severity (Risky vs. Alcohol Use Disorder) and 2 occasions (0 and 3 months) as the repeated measures design. We will take an intent-to-treat approach to the analysis; Veterans will be included in our primary analyses regardless of their level of adherence with their assigned intervention. Participants who do not complete the 3-month follow-up assessment will be considered to have missing data for that assessment and will not be included in the analysis of intervention effectiveness. The secondary outcomes, which will be “incidence rates”, will be tested by logistic regression.

Primary Hypothesis: The Relational Agent will be more effective than Treatment as Usual in reducing the quantity and frequency of alcohol use.

Our primary analyses of the effectiveness of Treatment as Usual vs. Treatment as Usual plus Relational Agent Intervention will focus on measurement outcome variables at the **3-month follow-up**. Separate analyses will be performed for the two primary outcome measures: number of drinking days per week (frequency) and average drinks per drinking day (quantity), both reported over a month. Here we describe the analytic approach for the outcome of quantity of alcohol use (average drinks per drinking day); the approach for frequency will be analogous. Initially our analysis will be through analysis of covariance models. We will include baseline values of the outcome variable as a covariate in these models, so our analyses may be interpreted as focusing on the change in outcome from baseline to three month follow-up. If any key characteristics of our sample were found to differ between groups, we will enter those as covariates as well.

Secondary Hypothesis: The Relational Agent will be more effective than Treatment as Usual in improving rates of brief intervention.

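### Chart review is timed to the 3-month interview and the completers-only rule does not exempt chart-derived outcomes, so randomised Veterans can be dropped from the brief-intervention and referral analyses without need

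*Combined protocol and SAP*

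**What the plan says.** All places are in the combined protocol and SAP.

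- **Review of the Computerized Patient Record System (CPRS):** this section sets the timing and scope of abstraction: "Upon completion of the 3-month follow-up interview, we will review the electronic health record of each enrolled Veteran-participant". The abstraction instruction adopted there looks back to the latest alcohol screening and gives no end date.
- **Research Measures and Schedule of Use (table):** CPRS extraction is marked only in the 3-month follow-up column.
- **Dependent Variables:** for brief intervention and referral, "these secondary dependent variables will be ascertained from review of CPRS". For the main analyses, "we will count brief intervention or referral as completed if they are ascertained from either source".
- **Three-Month Follow-up Interview:** on the telephone questions about brief intervention and referral, "this ascertainment will complement the documentation of brief intervention and referral that may be present in the computerized patient record system".
- **Statistical Analysis:** after declaring an intent-to-treat approach, the plan says: "Participants who do not complete the 3-month follow-up assessment will be considered to have missing data for that assessment", and that they "will not be included in the analysis of intervention effectiveness". The next sentence assigns the secondary outcomes to logistic regression. The later paragraphs on the two secondary hypotheses name no analysis population.
- **Eligibility Criteria:** inclusion requires "having a primary care provider at VA Boston PCC".

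No section gives a date or procedure for reviewing the chart of a Veteran who never completes the interview.

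**The concern.** The telephone interview is indispensable for the primary outcomes, which come from the Quick Drink Screen. It is not indispensable for the secondary ones. Every participant has a VA primary care provider, and the chart can be read whether or not the Veteran answers the telephone. An analyst who follows the exclusion sentence literally would still discard the non-completers, because it refers to effectiveness analysis in general.

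Three things are at stake:

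- **Intention to treat.** Both named secondary hypotheses would be tested in completers only, despite the declared approach. If drop-out differs by arm and is related to receiving counselling or referral, the comparison can be biased.
- **Precision.** Outcomes that could have been observed would be thrown away.
- **Length of observation.** Follow-up Procedures allows repeated calls, up to three letters and then contact through locators. If the review waits for the interview and the look-back has no end date, a Veteran reached late has longer to accumulate a recorded event than one reached on time.

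**Working it through.** **1. The plan's own counts.** Recruitment: "We will recruit a total of 180 Veterans from primary care clinics". Sample Size and Power Considerations uses 20%, 25% and 30% loss to follow-up.

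- 180 × (1 − 0.20) = 144 and 180 × (1 − 0.30) = 126. This reproduces the stated 126 to 144 completers.
- Veterans without the interview: 180 − 144 = 36 and 180 − 126 = 54.
- The same section cites 10% to 30% in prior studies and expects the lower end. At 10%, 18 are lost and 162 remain.

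The stated powers (0.84, 0.82, 0.78) concern the primary outcomes. A two-sided t-test with d = 0.5 gives 0.846, 0.825 and 0.795, within 0.02 of each. The plan states no power for the secondary outcomes.

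**2. Precision if the exclusion applies.** With the same rates, interval width is proportional to 1/√N, so using 180 instead of N narrows intervals by 1 − √(N/180).

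| Loss | N analysed | 1 − √(N/180) |
|---|---|---|
| 10% | 162 | 5.1% |
| 20% | 144 | 10.6% |
| 30% | 126 | 16.3% |

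**3. Power, as illustration only.** The documents give no brief-intervention or referral rates, so those below are assumed, with equal arms and two-sided alpha 0.05. The formula is Φ{[|p₂ − p₁|√n − 1.96√(2p̄(1 − p̄))] / √(p₁(1 − p₁) + p₂(1 − p₂))}, where n is the number per arm and p̄ the mean of the two rates.

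For 50% versus 70%, √(2p̄(1 − p̄)) = √0.48 = 0.693 and the denominator is √0.46 = 0.678. At n = 90: (0.2 × 9.487 − 1.96 × 0.693)/0.678 = 0.80, so power is 0.79.

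| Assumed rates | 63 per arm | 72 per arm | 90 per arm |
|---|---|---|---|
| 10% vs 25% | 0.60 | 0.66 | 0.76 |
| 20% vs 40% | 0.69 | 0.75 | 0.84 |
| 50% vs 70% | 0.63 | 0.69 | 0.79 |
| 70% vs 85% | 0.52 | 0.58 | 0.68 |

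If the contrast is large there is little to gain: at 50% versus 80%, power is 0.95 at 63 per arm and 0.99 at 90.

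**4. Bias, as illustration only.** Assume 80% versus 50% among completers, 60% versus 30% among non-completers, and drop-out of 30% with the Relational Agent and 20% with usual care. The completers' difference is 0.30. Among all randomised it is (0.8 × 0.7 + 0.6 × 0.3) − (0.5 × 0.8 + 0.3 × 0.2) = 0.74 − 0.46 = 0.28. With 40% among non-completers in both arms it is 0.68 − 0.48 = 0.20. With the first set of rates and 20% drop-out in both arms there is no bias (0.76 − 0.46 = 0.30).

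**The case against.** **The exclusion may not be intended.** The chart-review sentence covers each enrolled participant, so its opening words can describe timing and not a condition. The exclusion sentence speaks of data missing for that one assessment, and Study Design for Aim 2 describes the 3-month assessment of alcohol use as a telephone survey. Sources of Materials mentions CPRS data for the usual-care arm with no interview condition, and Follow-up Procedures already has staff opening the charts of Veterans they cannot reach. This stands. A reader might infer that the plan forbids chart review for non-completers; no sentence says so. But none says the opposite about the analysis population either, and the schedule table places extraction at the 3-month follow-up.

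**Lost numbers and unequal ascertainment do not occur together.** A reader might infer that the plan both drops non-completers and gives them only one chance, against two for completers, of being counted positive under the either-source rule. If non-completers are excluded, everyone analysed has both sources. If they are included, ascertainment is unequal but no numbers are lost. These are alternative readings, and each needs a rule.

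**CPRS alone is not clearly the better endpoint.** A reader might infer that it should replace the either-source definition as the main analysis. Under Relational Agent Intervention-procedure, the agent's clinic report goes into a CPRS progress note and study personnel place the consult. In usual care, documentation depends on the clinician. A chart-only endpoint may therefore miss undocumented counselling mainly in usual care and favour the intervention. Self-report can recover some of it, and the plan also intends a concordance check. This stands, and it is why the prespecified analysis should not be demoted.

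**The plan has a remedy for differential drop-out.** It would use inverse-probability-weighted estimating equations. These depend on baseline predictors of drop-out and would not put back outcomes that the chart can supply directly.

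**Conclusion.** The concern holds as an unresolved conflict in the text with a practical consequence. Followed literally, the completers-only rule can remove 36 to 54 of 180 Veterans (18 at 10% loss) from two secondary analyses whose data are obtainable without the interview. The wording does not make that reading certain.

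If the exclusion applies, analysing all 180 narrows confidence intervals by about 11% to 16% at 20% to 30% loss and about 5% at 10%, and makes the secondary analysis intention-to-treat. The 20% to 30% range comes from the plan's power table; the plan itself hopes for less. The power and bias figures rest on assumed rates. They also hold the rates fixed while the endpoint moves from either-source to chart-only, so they do not measure the gain from the fix exactly.

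The variable abstraction window needs correcting under either reading. The primary outcomes need the telephone interview and are unaffected.

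**What to change.** 1. State that CPRS is abstracted for every randomised Veteran over a fixed window of 3 months from randomisation, whether or not the interview took place. Because Recruitment lets the clinical encounter come before the baseline interview, state also whether counselling at an index visit that preceded randomisation counts.
2. Limit the exclusion sentence in Statistical Analysis to outcomes collected at the interview, and name the analysis population in the paragraphs on the two secondary hypotheses.
3. Report a CPRS-based analysis of brief intervention and referral in all randomised Veterans alongside the prespecified either-source analysis in interview completers. Keep the standing of the latter, and note that study staff generate part of the Relational Agent arm's chart documentation.

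The cost is at most 36 to 54 additional chart reviews at 20% to 30% loss (18 at 10%), and none if the team already meant to review everyone. The rest is wording. No new data collection from Veterans is needed.

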For this study, clinic staff will fill out the "Permission to Contact for Research" form with the veteran and pass it to the research assistant in clinic, or hold it in a predetermined place for the research assistant to pick up. If possible the research assistant will interview the patient during the visit. We will aim to have participants complete the baseline interview (and, for Veterans ultimately allocated to the Relational Agent arm, the Relational Agent interaction) prior to seeing their clinician for the scheduled clinical encounter; however, if workflow requires the Veteran to complete his encounter first, the research assistant will meet the Veteran immediately following the visit to complete the baseline interview. If necessary, the veteran will be scheduled for a return visit to finish the baseline interview and/or session 1. The research assistant will have a private space to conduct interviews and have the veteran use the Relational Agent program.

In addition, each week, clinic staff will provide us with a list of patients who are due for an AUD-C screening. We depend on staff to recruit and refer patients to us, and it has been slow going. 1. We would like to use CPRS to access the medical files of anyone who was supposed to be screened with the AUDIT-C that week. If the person scored positive on the AUDIT-C we will send them a letter containing a brief description of our study and an opt out card. If we do not receive an opt out card in the two weeks following the letter, our study team will try and contact the individual by phone to see if they would be interested in participating in the study. If they are interested, we will conduct the screening on the phone and, if eligible, we will schedule them for a baseline interview in person. 2.

Study flyers have been placed around the hospital with the study's telephone number around the hospital. To include veterans who call our study line directly, we would check their eligibility by directly administering the AUD-C over the phone. This AUD-C will not go into CPRS; it will stay in study records. Then we will follow our standard eligibility requirements and procedures.

Eligibility Criteria

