We will use these instructions and, as done by Hawkins et al, we will provide reviewers with examples that satisfy each of the above components of brief alcohol counseling. Similarly, we will follow the approach of Hawkins et al in ascertaining referral for alcohol problems. Referral to alcohol treatment will be defined as a documented discussion in CPRS of referral for VA or non-VA services to address alcohol misuse or a scheduled appointment for VA services. We will train reviewers to identify and abstract information of any referral to VA or non-VA alcohol treatment services and document type of referred services (e.g., addiction specialty care, non-VA primary care services?) and date of referral appointment. Alcohol treatment services will be defined as any of the following with documentation indicating the purpose of the service was to evaluate or address alcohol misuse: VA inpatient or outpatient specialty-care addiction services, VA alcohol-related telephone counseling, or referral to non-VA facility for alcohol treatment. Reviewers will also be instructed to indicate if a discussion of a treatment referral was documented in CPRS without actual referral being made. For Veterans who received appointments to address alcohol misuse, reviewers will ascertain the date Veterans attended their referral appointment.

In addition, we will abstract and record other Mental Health diagnoses, especially Substance Use Disorders, PTSD, and TBI, to describe the sample and examine any subgroup differences.

[name], an experienced primary care physician and active user of CPRS, will train the research assistants to conduct the CPRS review and abstraction. The research assistants will be blinded to the treatment status of the Veterans. [name], who will also be blinded to the treatment status, will oversee the data abstraction and ensure its quality and accuracy. Abstracted data will be entered into the REDCAP database for eventual conversion to SPSS format for analysis.

Study Data Management

Telephone communications. We will have one telephone line where participants or clinic staff can call and leave messages. Research staff will answer this phone or return calls promptly.

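### Brief intervention is counted from the last alcohol screening, not from randomisation, so care given before allocation can be scored and can dilute two secondary comparisons

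*Combined protocol and SAP*

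**What the plan says.** **Chart window.** The section on review of CPRS takes its abstraction wording from an earlier study: "At any time since the most recent alcohol screening, does the record document any of the following components". The plan adopts it ("We will use these instructions"). Abstractors also follow this direction: "Indicate all that apply and the date counseling was noted in the record". The rule for referral gives no start date. The dates listed for it are those of the appointment and of attendance, not the date the referral was made.

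**Interview window.** The Three-Month Follow-up Interview asks whether the Veteran "received brief intervention or referral for alcohol problems at the index primary care visit or in the intervening 3-month period". Under Dependent Variables, a positive answer from either source is enough.

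**Order of visit and randomisation.** Randomisation follows the baseline interview and stratification. Recruitment aims for baseline before the clinician encounter but allows other orders:
- Encounter first: "if workflow requires the Veteran to complete his encounter first, the research assistant will meet the Veteran immediately following the visit".
- Return visit: if necessary, "the veteran will be scheduled for a return visit to finish the baseline interview and/or session 1".
- Letter, for Veterans already screened positive in CPRS: "If we do not receive an opt out card in the two weeks following the letter, our study team will try and contact".
- Flyer, with a study screen taken by telephone: "This AUD-C will not go into CPRS; it will stay in study records".

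**Stated time point.** The Rationale says that rates of brief intervention and referral are measured three months after randomisation.

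**The concern.** Treatment as Usual (TAU) is described as the primary care clinician responding to a positive screen, with an electronic reminder to deliver a brief intervention. For a Veteran whose clinic visit is over before baseline, that response may already have happened. The chart rule and the interview item both include it, and nothing in the plan removes it.

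An event that precedes allocation cannot be caused by allocation. Counting it adds a similar share of positives to each arm and reduces the contrast that the two secondary hypotheses test. The window also contradicts the Rationale, so two analysts could build different outcomes from the same plan.

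**Working it through.** **1. Which entry routes are affected**

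| Route | Where the clinic visit or last CPRS screen falls | Can care before allocation be scored? |
|---|---|---|
| Baseline first, as intended | Screen just before baseline, encounter after randomisation | Little room for it |
| Encounter first | Same day, before randomisation | Yes, by chart and interview |
| Return visit for baseline | Earlier day, if the encounter took place at the first visit | Yes, by chart and interview |
| Letter | Screen more than two weeks before the first call, baseline later still | Yes, by chart; by interview if the screening visit is taken as the index visit |
| Flyer | Last CPRS screen is a clinic screen; screening is annual, so it may be months old | Yes, by chart, if the window runs from the CPRS screen |

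The documents do not give the share of Veterans entering by each route.

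**2. Is there a stated figure to reproduce?** No. Sample Size and Power Considerations covers only the two drinking outcomes. No event rate or power is given for brief intervention or referral.

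**3. Size of the dilution.** Let q be the share in each arm already counselled between screening and randomisation, and p the chance of brief intervention after randomisation. If the two are independent:

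- scored rate = q + (1 − q)p = 1 − (1 − q)(1 − p)
- scored difference = (1 − q)(p_RA − p_TAU)

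Without independence, the scored difference is (1 − q) times the difference among Veterans not counselled before randomisation.

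**4. Power at 72 per arm.** This is the 20% loss row of the plan's power table. Two-sided alpha of 0.05 is assumed, because the plan gives 0.05 without sidedness. By the arcsine approximation, h = 2·asin√p_RA − 2·asin√p_TAU and power ≈ Φ(h√(72/2) − 1.96) = Φ(6h − 1.96). All event rates and q are assumptions. For example, q = 0.30 arises if half of Veterans have the encounter first and 60% of those are counselled there (0.5 × 0.6).

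| Rates after randomisation | q | Scored rates | Difference | h | Power |
|---|---|---|---|---|---|
| 50% vs 70% | 0 | 50% vs 70% | 20 points | 0.412 | 0.70 |
| 50% vs 70% | 0.30 | 1 − 0.7×0.5 = 65% vs 1 − 0.7×0.3 = 79% | 14 points | 0.314 | 0.47 |
| 50% vs 90% | 0.30 | 65% vs 1 − 0.7×0.1 = 93% | 28 points (from 40) | 0.731 | 0.99 |

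**5. Other assumed values.** With 90 per arm (180/2, if charts are reviewed for everyone), the normal approximation with pooled variance under the null gives, for 30% vs 50%, power of 0.79, 0.58, 0.39 and 0.24 at q = 0, 0.2, 0.4 and 0.6. For 30% vs 90%, power stays at or above 0.99 up to q = 0.6, but the difference falls from 60 to 24 points (0.4 × 60).

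**6. What a post-randomisation window does to the TAU rate.** Assume half of TAU Veterans have the encounter first, 60% are counselled at the visit in either order, and encounter-first Veterans have a 10% chance of later counselling.

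- Since screening: 0.5×0.60 + 0.5×(0.60 + 0.40×0.10) = 62%
- Since randomisation: 0.5×0.60 + 0.5×0.10 = 35%

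Changing the window alone moves the TAU rate by 27 points under these assumptions, so the choice has to be stated.

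**The case against.** The strongest reply is that the plan has chosen a different estimand: whether a Veteran who screened positive was counselled during that episode of care. The interview item names the index visit, and TAU is defined as the clinician's response to the screen. On that reading the index visit belongs to the comparator, and the between-arm difference is a valid intention-to-treat effect. This may cover a visit on the day of enrolment. It does not cover counselling weeks or months before enrolment on the letter and flyer routes, and it does not fit the time point in the Rationale.

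Three further points stand:

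- A post-randomisation rule is not neutral. For encounter-first Veterans it removes TAU's main opportunity for brief intervention, while the Relational Agent session always follows randomisation and is noted in CPRS.
- The contrast may be large. If session 1 itself counts as a brief intervention, the Relational Agent rate could be near 90% and power would survive.
- Counselling dates are already abstracted, so a post-randomisation chart count is available apart from same-day ordering. Self-report and the date a referral was made are not covered in this way.

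A reader might infer that the window biases the trial towards a false positive, or that power is known to fall to 0.47. The documents support neither. Randomisation balances earlier care in expectation, and the 0.47 rests on rates that the plan does not give.

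**Conclusion.** The concern holds as a mismatch between the outcome window and the time of randomisation. Care given before allocation can be scored from either source for encounter-first, return-visit, letter and flyer recruits, and no rule excludes it. The consequence is dilution of the risk difference by about (1 − q), assuming later care is independent of earlier care. Type I error is not inflated.

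The loss of power cannot be determined from the documents. In the examples at q = 0.30 and 72 per arm, it ranges from substantial (0.70 to 0.47) to negligible (0.99 retained), depending on the assumed contrast. The reported effect shrinks in either case.

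The point concerns the secondary outcomes of brief intervention and referral. The two primary drinking outcomes, taken from the Quick Drink Screen, are unaffected. It should be settled before chart abstraction and the 3-month calls, because undated self-report cannot be repaired afterwards.

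**What to change.** 1. Define brief intervention and referral as events from randomisation to 3 months. Use the counselling date already abstracted, add the date each referral was made, and anchor the interview question to the enrolment date. Where the event falls on the day of randomisation, record its time or order.
2. Record whether the index encounter came before or after randomisation. Include this as a covariate in the logistic model and report results by encounter order.
3. State whether a same-day index visit before randomisation is part of the TAU comparison, and report the since-screening count as a sensitivity analysis. This shows how far the result depends on removing that visit from TAU.

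The cost is a few abstraction and REDCap fields and a change to the interview script. The remaining weakness is that same-day events reported by Veterans three months later will be harder to place before or after randomisation.
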